13.8 Analysis of Secondary Endpoints

Safety and Tolerability: All adverse events recorded during the trial will be summarized for the safety population. The incidence of events that is new or worsening from the time of first dose of treatment will be summarized according to system organ class term, severity (based on CTCAE version 4.0 grade), type of adverse event, and relation to study treatment. For the combination therapy, special interests include toxicities related to induction of immune phenomenon such as pneumonitis, colitis, and severe rash. The frequency of AEs will be summarized separately according to treatment arms, with 90% exact binomial confidence intervals (CI). The proportion of patients in each arm with grade 4 or higher AEs will also be reported with an exact binomial 90% CI.

Deaths reportable as SAEs and non-fatal serious adverse events will be listed by patient and tabulated by primary system organ class, and type of adverse event.

PFS and OS: The distributions of time to PSA progression, PFS and OS will each be summarized using the product-limit method of Kaplan-Meier according to treatment arms. Median times for each endpoint will be presented with two-sided 95% confidence intervals estimated using log(-log(survival)) methodology. Kaplan-Meier estimates of the endpoints at 6 or 12 months after treatment initiation may also be presented with two-sided 95% confidence intervals.

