5.4 Criteria for Taking a Participant Off Protocol Therapy

Duration of therapy will depend on individual response, evidence of disease progression and tolerance. In the absence of treatment delays due to adverse event(s) or the scheduled break after the first 3 doses of radium-223 in arm A, treatment may continue for up to a total of 6 doses of radium-223 and up to 35 doses (24 months) of pembrolizumab if achieving clinical benefit and tolerating or until one of the following criteria applies:

- Disease progression
 - Arm A:
 - After 3 months on study therapy (generally week 12 re-staging scans)
 - If the patient has stable disease or better, they will start on a radium-223 break, but continue on pembrolizumab.
 - If there have been treatment delays, the break should not commence until at least 3 doses of radium are given unless the radium-223 is deemed intolerable/toxic.
 If pembrolizumab has been discontinued due to toxicity despite stable disease or better, radium-223 will be continued without a break, and study assessments will be conducted on the same schedule as Arm B.

- Due to the intricacies of assessing response/progression in bone only disease, in cases where the treating investigator feels the patient is clinically benefiting from the radium-223 and that a break would be harmful to disease control, omission of the break will be permitted on a case-by-case basis after discussion with the PI. These patients will be continued on the radium-223 every month without break as is standard of care. Study assessments during combination therapy will continue per the required data table in Arm A. Scans will continue to adhere to the study schedule (every 12 weeks). Alternatively, the patient or clinician may choose to stop study therapy and proceed with alternative systemic therapies at their discretion.
- If 2 or more new bone lesions ("unconfirmed progression") are present on initial scans and the patient has received all 3 initial doses, radium-223 should be continued until reassessment with confirmatory scans ≥ 6 weeks.
- If "unconfirmed progression" of nodal disease occurs, but no new visceral disease, the patient may continue on pembrolizumab and radium-223 until reassessment with confirmatory scans ≥ 6 weeks or be discontinued per treating investigator's discretion.

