- For patients with unconfirmed bone or nodal progression who continue on study therapy after initial restaging scans (~12 weeks), if subsequent scans (at least ≥ 6 weeks from initial scans) show:
 - The disease has stabilized or improved: they may continue on study therapy until disease progression or until intolerability/toxicity precludes further administration.
 - Continued radiologic progression per RECIST v1.1 or PCWG2: the patient should be discontinued from study therapy. If the treating investigator believes the patient is clinically benefiting, continuation of one or both study drugs may be permitted upon discussion with PI.
- If there is evidence of new visceral disease at any point, the patient should be discontinued from both agents.
- For all subsequent scans of patient who commence on radium-223 break:
 - If the patient continues to have stable disease or better, they will continue on pembrolizumab alone.
 - If the patient went on radium-223 break, it may be restarted:
 - Whenever the patient meets progressive disease criteria per

protocol as long as there is no new visceral disease. No confirmatory scans are required unless the treating investigator prefers to wait to confirm before restarting. The rationale to allow restarting of radium-223 in patients who are progressing in the nodes is the possible role of radium-223 as an immune modulator that may help stimulate the immune response to pembrolizumab.

- In cases where treating investigator feels that patient would clinically benefit from restarting radium-223, even though not technically progressing by RECIST v 1.1 or PCWG2, will be discussed and permitted only on a case-by-case basis with the PI.
- If the patient meets protocol criteria for disease progression on the next scheduled scans after restarting radium-223 (and has received at least 2 more doses of radium-223), they should be discontinued from study therapy. If they do not meet these criteria or treating investigator believes they are clinically benefiting, they may be permitted to continue on a case-bycase basis after discussion with the PI. Similarly, if treating physician feels the patient is clinically progressing prior to 2 more doses of radium-223, the patient can be discontinued from study therapy.
- If patient has signs of new visceral disease at any time meeting RECIST v1.1 criteria, they will be discontinued from study therapy.
- For subsequent scans of patients who do not commence on radium-223 break:

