 - If the patient continues to have stable disease or better, they will continue on combination study therapy.
 - If scans show progressive disease per protocol criteria, they should discontinue therapy. In cases where treating investigator feels that the patient would clinically benefit from continuing study therapy even though they are technically progressing by RECIST v1.1 or PCWG2, continuation will be discussed on a case-by-case basis with the PI.
- Arm B
 - Continue on radium-223 until the patient meets protocol criteria for disease progression, up to a maximum of 6 doses.
- Intercurrent illness that prevents further administration of treatment

- Unacceptable adverse event(s)
- Participant demonstrates an inability or unwillingness to comply with the documentation requirements
- Participant decides to withdraw from the protocol therapy
- General or specific changes in the participant's condition render the participant unacceptable for further treatment in the judgment of the treating investigator
- Completed 24 months of uninterrupted treatment with pembrolizumab or 35 administrations of study medication, whichever is later. *Note: 24 months of study medication is calculated from the date of first dose.*

Participants will be removed from the protocol therapy when any of these criteria apply. The reason for removal from protocol therapy, and the date the participant was removed, must be documented in the case report form (CRF). Alternative care options will be discussed with the participant.

An ODQ Treatment Ended/Off Study Form will be completed when a participant is removed from protocol therapy. This form can be found on the ODQ website or obtained from the ODQ registration staff.

In the event of unusual or life-threatening complications, treating investigators must immediately notify the Overall PI,

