5.5 Duration of Follow Up

Participants will have a follow up visit within 30 days of removal from protocol therapy (End of Treatment visit). Adverse event monitoring will continue through End of Treatment visit. Subjects who discontinue for reasons other than progressive disease will have post-treatment follow-up for disease status until disease progression, initiating a non-study cancer treatment, withdrawing consent or becoming lost to follow-up. Follow up scans are not required for patients who do not progress, but will be captured if possible. After documented disease progression each subject will be followed by telephone, chart review, or clinic visit for overall survival until death, withdrawal of consent, or the end of the study, whichever occurs first. Regardless of reason for discontinuation, patients will be followed every 6 months until death or 2 years after treatment discontinuation.

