7. ADVERSE EVENTS: LIST AND REPORTING REQUIREMENTS

Adverse event (AE) monitoring and reporting is a routine part of every clinical trial. The following list of reported and/or potential AEs (Section 7.1) and the characteristics of an observed AE (Section 7.2) will determine whether the event requires expedited reporting **in addition** to routine reporting.

An adverse event is defined as any untoward medical occurrence in a patient or clinical investigation subject administered a pharmaceutical product and which does not necessarily have to have a causal relationship with this treatment. An adverse event can therefore be any unfavorable and unintended sign (including an abnormal laboratory finding, for example), symptom, or disease temporally associated with the use of a medicinal product or protocol-specified procedure, whether or not considered related to the medicinal product or protocol-specified procedure. Any worsening (i.e., any clinically significant adverse change in frequency and/or intensity) of a preexisting condition that is temporally associated with the use of the Merck's product, is also an adverse event.

Adverse events may occur during the course of the use of Merck product in clinical trials or within the follow-up period specified by the protocol, or prescribed in clinical practice, from overdose (whether accidental or intentional), from abuse and from withdrawal.

Adverse events may also occur in screened subjects during any pre-allocation baseline period as a result of a protocol-specified intervention, including washout or discontinuation of usual therapy, diet, placebo treatment or a procedure.

Progression of the cancer under study is not considered an adverse event unless it is considered to be drug related by the investigator.

All adverse events will be recorded from the time the consent form is signed through 30 days following cessation of treatment and at each examination on the Adverse Event case report forms/worksheets.

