A: All baseline evaluations are to be conducted within 42 days prior to treatment initiation. In the event that the participant's condition is deteriorating, laboratory evaluations should be repeated within 48 hours prior to initiation of the next cycle of therapy. D1 labs and assessments do not need to be performed if have been done within 72hrs prior to study drug dosing. C1D1 labs do not need to re-meet eligibility criteria but do need to meet criteria as detailed in Section 5.2.1.

B: Physical examination should include general description of participant, head, eyes, and throat, chest, abdominal, extremities, neurologic, skin, and lymph node examination. Any other evaluation is up to the discretion of the practitioner. It will not be considered a violation if the exam is not described as outlined here. Patient will be seen in clinic the day of any study drug infusion (e.g., radium-223 and/or pembrolizumab)

C: Vital signs included blood pressure, heart rate, respiratory rate, body temperature

D: CBC with differential should be done before each dose of radium-223 and pembrolizumab.

E: Serum chemistry to include full CMP with sodium, potassium, chloride, bicarbonate, BUN, creatinine, glucose, calcium, albumin. Liver function tests to include AST, ALT, total bilirubin and direct bilirubin, alkaline phosphatase.

F: PSAs should be done at baseline, week 1 day 1 (per treating investigator's discretion), every 4-6 weeks on therapy, and at study end.

G: TSH, Free T4 to be done a baseline, week 4 (week 5 for arm B), week 13, and then approximately every 12 weeks.

H: Coagulation factors to include PT and INR.

I: Pembrolizumab will be given by IV every 3 weeks (+/- 3 days) in Arm A only.

J: Radium-223 will be given by IV every 4 (+/- 7 days) weeks for a maximum of 6 doses.

Arm A: Radium-223 will be held after 3 doses. It may be restarted (to complete the final doses up to a maximum of 6 from study start) when there is progressive disease in bones as long as there is no new visceral disease.

Arm B: Radium-223 will be given as per standard of care monthly for 6 months in a row without breaks except for toxicity/intolerance as detailed in Section 6.2.

K: Adverse events will be monitored continuously

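### Adverse events are collected for about twice as long in Arm A as in Arm B, yet 13.8 gives only crude frequencies by arm; the rules for scans after treatment also conflict

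*Combined protocol and SAP*

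**What the plan says.** **Collection of adverse events.** Section 7: "All adverse events will be recorded from the time the consent form is signed through 30 days following cessation of treatment". Section 5.5: "Adverse event monitoring will continue through End of Treatment visit", with that visit set within 30 days of leaving therapy. Two longer windows exist. Under 7.3 and 7.4, serious events and events of clinical interest run to 90 days after treatment, shortened if new anticancer therapy starts. Under 7.3, fractures are reported for at least a year after the last radium-223 dose. Both are still counted from the patient's own last dose.

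**Length of treatment.** Section 5.4 allows "up to a total of 6 doses of radium-223 and up to 35 doses (24 months) of pembrolizumab". For Arm B: "Continue on radium-223 until the patient meets protocol criteria for disease progression, up to a maximum of 6 doses". Calendar footnote J: "Arm A: Radium-223 will be held after 3 doses"; pembrolizumab goes on through that break. For progression after the break, 5.4 adds: "If the patient went on radium-223 break, it may be restarted". The pembrolizumab limit is the later of 24 months and 35 administrations, so 24 months is not a hard ceiling.

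**Analysis.** Section 13.8: "The frequency of AEs will be summarized separately according to treatment arms, with 90% exact binomial confidence intervals (CI". It treats grade 4 or higher events in the same way. It names no person-time rate, time to first event or common cut-off for adverse events.

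**Scans after treatment.** Section 5.5 first asks for disease-status follow-up until progression in patients who stop for another reason, and then says: "Follow up scans are not required for patients who do not progress, but will be captured if possible". Section 11.1 and footnote L set 12-weekly imaging with no stated end. Footnote R runs Arm B assessments up to six doses, and footnote Q lists post-treatment follow-up without imaging. Under 13.1, PFS is censored at the last disease evaluation, and 13.8 may present it at 6 or 12 months.

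**The concern.** A binomial proportion treats every patient as equally observed. Here one arm has a fixed short course and the other an open-ended one, and the collection window follows the course. Arm A can therefore show more patients with an event at the same monthly risk, including for the treatment-related grade 3 or higher endpoint in 13.1. Arm B is the only concurrent group against which a reader can set the combination, for which 13.5 says there are no safety data.

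The scan rules raise a similar problem for PFS. Arm A patients on pembrolizumab keep a 12-weekly imaging schedule. Arm B patients finish at about week 21, and the documents do not settle whether they must be imaged at week 24 or later.

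**Working it through.** **1. The plan's own figure.** 35 doses × 21 days = 735 days = 24.1 months, which agrees with the stated 24 months.

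**2. Maximum windows for routine events, no delays, counted from the first dose.**
- Arm B: the sixth dose is at 5 × 28 = 140 days; 140 + 30 = day 170. If every interval uses its +7 days, 175 + 30 = day 205.
- Arm A: the 35th dose is at 34 × 21 = 714 days; 714 + 30 = 744 days = 24.4 months.

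**3. Typical windows.** Assume that time on treatment T is exponential with the same median in both arms, capped at c = 24 months (Arm A) or 140/30.4375 = 4.60 months (Arm B). A 6-month median appears in 13.11 for PFS; using it for time on treatment is my assumption. Let μ = ln 2/6 = 0.1155 per month and w = 30/30.4375 = 0.986 months.

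Mean window = (1 − e^(−μc))/μ + w
- Arm A: 8.115 + 0.986 = 9.10 months
- Arm B: 3.568 + 0.986 = 4.55 months

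The ratio is about 2. If data are also cut at 6 to 24 months after entry (uniform, from the accrual and follow-up in 13.2), the Arm A mean falls to 7.6 months and Arm B hardly changes.

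**4. Crude frequency at equal risk.** With an assumed constant hazard h = 0.05 per month in both arms:

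Frequency = 1 − e^(−hw) × [μ + h·e^(−(h+μ)c)]/(h + μ)
- Arm A: 1 − 0.9519 × 0.7036 = 33%
- Arm B: 1 − 0.9519 × 0.8390 = 20%

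With a 90-day window (w = 2.957, e^(−hw) = 0.8626), the results are 39% and 28%. The ratio falls from 1.64 to 1.42, and the difference stays near 12 to 13 points.

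| Assumption changed | Arm A | Arm B |
|---|---|---|
| Median 4 months | 26% | 18% |
| Median 12 months | 46% | 22% |
| Hazard 0.02 (median 6) | 16% | 9% |
| Hazard 0.10 (median 6) | 51% | 36% |
| Cut from 13.2, medians 4 / 6 / 12 | 24 / 30 / 38% | 18 / 20 / 22% |

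**5. Do other summaries remove the gap?** By simulation at a 6-month median:
- Constant hazard: first events per patient-month are 0.050 in both arms. Cumulative incidence at day 170 is 24% in both, matching 1 − e^(−0.05 × 170/30.4375) = 24.4%.
- Half of Arm A treated for 3 months past progression: crude 38% v 20%. A simple count to day 170 is still unequal (22% v 20%), but the cumulative incidence is 24% in both.
- Front-loaded hazard (0.10 for 3 months, then 0.02): crude 32% v 27%. The rate is 0.050 v 0.072, which now flatters Arm A. The cumulative incidence is 30% in both.

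The rate alone can mislead, so both summaries are needed.

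**6. PFS.** Week 24 is day 168, with a window of day 161 to 175. Six months is 6 × 30.4375 = day 182.6. A patient last scanned at week 24 is censored 182.6 − 175 = 7.6 to 182.6 − 161 = 21.6 days before the 6-month estimate. With exponential PFS, the event-free share at week 24 is e^(−ln 2 × 5.52/median): 38%, 53% and 73% for medians of 4, 6 and 12 months. That is about 6, 8 or 11 of 15 Arm B patients.

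**The case against.** The strongest reply is that no comparison is planned, so none is broken. The safety objective is to assess the combination. 13.8 summarises the arms separately without a test, and the early rule in 13.5 judges Arm A against an absolute rate after 12 weeks. A crude frequency also answers a fair question: how many patients on each regimen, as given, had an event. More events on a longer regimen are a real burden. All of this stands. It is why the crude table should stay and why the point concerns secondary reporting only.

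The hazards are assumed. A common constant hazard is a simplification when the drugs differ by arm and by phase, so the sizes are illustrations. Precision is also low: 10 of 30 has an exact 90% interval of 19% to 50%, and 3 of 15 has 6% to 44%.

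Part of the scan conflict could be a matter of scope, with 5.5 governing post-treatment follow-up and 11.1 and footnote L the on-treatment period. That reading does not resolve the two statements inside 5.5.

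Three stronger readings are tempting and unsupported:
- That observation typically differs as 24 months does from day 170. Those are schedule maxima; the modelled difference is about twofold.
- That all adverse event data stop at 30 days. Serious events, events of clinical interest and fractures run longer.
- That no event-free Arm B patient can contribute to PFS after week 24. Later scans are kept when available, and a later death counts as a PFS event.

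**Conclusion.** The point holds as a matter of secondary, descriptive reporting. The unequal windows follow directly from the protocol, and the direction of the crude gap at equal risk needs only that Arm A is observed longer. Its size, 33% v 20% in the central illustration and 39% v 28% with a 90-day window, rests on an assumed constant hazard of 0.05 per month, a 6-month median and the same time-on-treatment distribution before the caps. It does not show that the combination's safety results will be wrong.

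The scan passages do conflict, most clearly within 5.5. If scans after treatment are optional, event-free Arm B patients with no further captured scan are censored at about week 24, or earlier if that scan is not required either. The counts out of 15 assume that all randomised Arm B patients enter the PFS summary. 13.12.2 supports this, but 13.6 would restrict the summary to patients with paired biopsies.

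**What to change.** **Adverse events (13.8).** Keep the crude table as the description of total regimen burden and show collection time by arm beside it. Add:
1. Exposure-adjusted incidence by arm: patients with a first event divided by patient-months of collection up to that event, including treatment-related grade 3 or higher events.
2. Cumulative incidence of first event through about day 170, censoring each patient at the end of his own collection window, with death as a competing event.

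For serious events, events of clinical interest and fractures, use the matching longer window so that later Arm B events are not dropped. Note beside the curve that radium-223 exposure by day 170 differs: three doses for an Arm A patient on the break, up to six in Arm B.

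**Scans.** Reconcile 5.5, 11.1 and footnotes L, Q and R, and state whether the week-24 and later scans are required in both arms. If they stay optional, give by-arm PFS at the nominal week-24 assessment rather than at 6 calendar months, and label later estimates as resting on unequal imaging.

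**Cost.** SAP wording, a few extra tables from dates already collected, and a clarification of the scan text. The new tables will be imprecise. The rate assumes a roughly constant hazard, and the curve assumes that stopping is unrelated to later risk. If the week-24 scan is not required in Arm B, the comparable PFS summary shrinks to week 12.

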5.2.2 Subsequent Cycles

- Day 1 complete metabolic panel and complete blood count (CBC) with differential must be reviewed by study staff prior to treatment to ensure they meet criteria as detailed in Section 6
 - Other labs such as thyroid function tests that may take longer to result do not have to be reviewed prior to the dose
- CBC with differential should be obtained prior to each dose of radium-223 or pembrolizumab and doses given only if eligible per guidelines in Section 6
- Day 1 assessments may be performed within 72 hours prior to study drug administration.

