7.1.1.2 Adverse Events Expected with Radium-223³

Bone Marrow Suppression

In the randomized phase 3 trial, 2% of patients on the radium-223 arm experienced bone marrow failure or ongoing pancytopenia compared to no patients treated with placebo. There were two deaths due to bone marrow failure and for 7 of 13 patients treated with radium-223, bone marrow failure was ongoing at the time of death. Among the 13 patients who experienced bone marrow failure, 54% required blood transfusions. Four percent (4%) of patients on the radium-223 arm and 2% on the placebo arm permanently discontinued therapy due to bone marrow suppression.

In the randomized trial, deaths related to vascular hemorrhage in association with myelosuppression were observed in 1% of radium-223-treated patients compared to 0.3% of patients treated with placebo. The incidence of infection-related deaths (2%), serious infections (10%), and febrile neutropenia (<1%) were similar for patients treated with radium-223 and placebo. Myelosuppression; notably thrombocytopenia, neutropenia, pancytopenia, and leukopenia; has been reported in patients treated with radium-223. In the randomized trial, complete blood counts (CBCs) were obtained every 4 weeks prior to each dose and the nadir CBCs and times of recovery were not well characterized. In a separate single-dose phase 1 study of radium-223, neutrophil and platelet count nadirs occurred 2 to 3 weeks after radium-223 administration at doses that were up to 1 to 5 times the recommended dose, and most patients recovered approximately 6 to 8 weeks after administration.

Clinical Trials Experience

In the randomized clinical trial in patients with metastatic castration-resistant prostate cancer with bone metastases, 600 patients received intravenous injections of 50 kBq/kg (1.35 microcurie/kg) of radium-223 and best standard of care and 301 patients received placebo and best standard of care once every 4 weeks for up to 6 injections.² Prior to randomization, 58% and 57% of patients had received docetaxel in the radium-223 and placebo arms, respectively. The median duration of treatment was 20 weeks (6 cycles) for radium-223 and 18 weeks (5 cycles) for placebo.

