The most common adverse reactions ($\geq 10\%$) in patients receiving radium-223 were nausea, diarrhea, vomiting, and peripheral edema. Grade 3 and 4 adverse events were reported among 57% of radium-223-treated patients and 63% of placebo-treated patients. The most common hematologic laboratory abnormalities in radium-223-treated patients ($\geq 10\%$) were anemia, lymphocytopenia, leukopenia, thrombocytopenia, and neutropenia.

Treatment discontinuations due to adverse events occurred in 17% of patients who received radium-223 and 21% of patients who received placebo. The most common hematologic laboratory abnormalities leading to discontinuation for radium-223 were anemia (2%) and thrombocytopenia (2%).

The Table below shows adverse reactions occurring in $\ge 2\%$ of patients and for which the incidence for radium-223 exceeds the incidence for placebo.

 Table 12: Adverse Reactions in the Randomized Trial of Radium and best standard of care vs. placebo and best standard of care

System/Organ Class	Xofigo	(n=600)	Placebo	o (n=301) Grades 3-4 %	
Preferred Term	Grades 1-4 %	Grades 3-4 %	Grades 1-4 %		
Blood and lymphatic sys	tem disorders	6		20 10	
Pancytopenia	2	1	0	0	
Gastrointestinal disorde	rs				
Nausea	36	2	35	2	
Diarrhea	25	2	15	2	
Vomiting	19	2	14	2	
General disorders and a	dministration site con	ditions	5. 		
Peripheral edema	13	2 10		1	
Renal and urinary disor	ders	d.	85	3.	
Renal failure and 3 mpairment		1	1	1	

Laboratory Abnormalities

The Table below shows the hematologic laboratory abnormalities occurring in $\geq 10\%$ of patients and for which the incidence for radium-223 exceeds the incidence for placebo.

Table 13: Hematologic Laboratory Abnormalities

Hematologic	Xofigo	(n=600)	Placebo (n=301)			
Laboratory Abnormalities	Grades 1-4 %	Grades 3-4 %	Grades 1-4 %	Grades 3-4 %		
Anemia 93		6	88	6 7		
Lymphocytopenia	mphocytopenia 72		53			
Leukopenia	35	3	10	<1		
Thrombocytopenia	31	3	22	<1		
Neutropenia	18	2	5	<1		

Laboratory values were obtained at baseline and prior to each 4-week cycle.

As an adverse reaction, grade 3-4 thrombocytopenia was reported in 6% of patients on radium-223 and in 2% of patients on placebo. Among patients who received radium-223, the laboratory abnormality grade 3-4 thrombocytopenia occurred in 1% of docetaxel naïve patients and in 4% of patients who had received prior docetaxel. Grade 3-4 neutropenia occurred in 1% of docetaxel naïve patients and in 3% of patients who have received prior docetaxel.

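### Through week 13 Arm A has twice Arm B's scheduled post-baseline CBCs, two in the stated nadir window, so by-arm neutropenia and thrombocytopenia rates are not like for like

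*Combined protocol and SAP*

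**What the plan says.** Section 13.8 summarizes all AEs recorded during the trial: "The frequency of AEs will be summarized separately according to treatment arms, with 90% exact binomial confidence intervals (CI". It does not restrict to visits shared by the arms and does not mention how often each arm is assessed. The safety endpoint in Section 13.1 is treatment-related AEs of grade 3 or higher, and Section 7 allows an abnormal laboratory finding to be an AE.

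Blood counts follow dosing. Section 5.2.2: "CBC with differential should be obtained prior to each dose of radium-223 or pembrolizumab". Study Calendar footnote D: "CBC with differential should be done before each dose of radium-223 and pembrolizumab". The two drugs run on different clocks. Footnote I: "Pembrolizumab will be given by IV every 3 weeks (+/- 3 days) in Arm A only". Footnote J: "Radium-223 will be given by IV every 4 (+/- 7 days) weeks for a maximum of 6 doses". The calendar marks weeks 4, 7 and 10 as Arm A only, with a CBC at each.

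On timing, Section 7.1.1.2 reports from a single-dose phase 1 study, at up to 1 to 5 times the recommended dose, that "neutrophil and platelet count nadirs occurred 2 to 3 weeks after radium-223 administration" and that "most patients recovered approximately 6 to 8 weeks after administration". The note to Table 13, for the phase 3 trial, reads "Laboratory values were obtained at baseline and prior to each 4-week cycle". The same section concedes that this 4-weekly pre-dose sampling left the nadir poorly characterized.

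**The concern.** Arm B is sampled on essentially the schedule that the protocol says misses the nadir. Arm A is sampled on that schedule plus the pembrolizumab visits. If both arms had exactly the same marrow response to radium-223, the arm with more counts, some taken nearer the low point, would record the worse grades.

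Safety of the combination is the first secondary objective (Section 1.3), and Section 13.5 notes that no safety data for the combination exist. Readers will compare the two columns of the AE table. An excess of neutropenia or thrombocytopenia in Arm A could be read as pembrolizumab worsening radium-223 myelosuppression when part or all of it reflects when blood was drawn.

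**Working it through.** The plan states no CBC count per arm, so there is no figure to reproduce. The counts below come from the Study Calendar and footnotes D, I and J.

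**Step 1: visit grid.** Week w begins on day 7(w − 1) + 1. Radium-223 doses 1 to 3 fall in weeks 1, 5 and 9, which are days 1, 29 and 57.

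| Week | Day | Days since last radium-223 dose | CBC in Arm A | CBC in Arm B |
|---|---|---|---|---|
| 4 | 22 | 22 − 1 = 21 | yes | no |
| 5 | 29 | 29 − 1 = 28 | yes | yes |
| 7 | 43 | 43 − 29 = 14 | yes | no |
| 9 | 57 | 57 − 29 = 28 | yes | yes |
| 10 | 64 | 64 − 57 = 7 | yes | no |
| 13 | 85 | 85 − 57 = 28 | yes | yes |

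That is 6 post-baseline CBCs against 3, a ratio of 2. Days 14 to 21 are sampled after doses 1 and 2 in Arm A and after no dose in Arm B. Neither arm samples that window after dose 3, because week 10 is only day 7.

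**Step 2: direction.** Arm B's scheduled times are a subset of Arm A's. For the same underlying course of counts, the worst grade over the larger set is at least as bad as the worst over the subset. In this period the recorded Arm A grade can therefore only be equal or worse. No model is needed for this.

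**Step 3: size, which needs assumptions.** Assume that each dose causes a linear fall to a nadir and a linear recovery, that falls from successive doses add, and that depth is lognormal between patients with log SD 0.6. Let R be the deepest relative fall seen at Arm A's visits divided by that at Arm B's. If Arm B's recorded rate is 3%, Arm A's rate without measurement noise is 1 − Φ(1.881 − ln R / 0.6).

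- Counts at day 28 as low as at nadir: R = 1, giving 3%, so no excess.
- Nadir day 21, recovery day 56: Arm A's deepest is week 7, 14/21 + 14/35 = 1.067; Arm B's is 28/35 = 0.8. R = 1.33, giving 1 − Φ(1.401), about 8%.
- Nadir day 14, recovery day 42: Arm A's deepest is week 7, 1.0; Arm B's is 14/28 = 0.5. R = 2, giving 1 − Φ(0.726), about 23%.

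A simulation of the same model with falling-and-recovering counts, adding measurement noise, gave about 7% to 23%. The 3% is borrowed from Table 13 (grade 3-4 thrombocytopenia), which covers up to six injections and a median of 20 weeks, not three CBCs. The range shows only how strongly the answer depends on the shape of recovery.

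**The case against.** Several points limit the finding.

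- *Whole-trial direction.* Section 13.8 covers the whole trial. After about week 12 Arm A normally pauses radium-223 while Arm B continues to six doses, and Section 2.3 says inadequate counts are a problem particularly in later cycles. A reader might infer that Arm A's rates will look higher over the whole trial. The documents do not support that, because later Arm B doses push the other way. This stands.
- *All hematologic toxicity.* The nadir statement covers neutrophils and platelets only. Extending it to anemia or lymphocytopenia, the commonest abnormalities in Table 13, is not supported. It also comes from single doses up to several times the recommended one. This stands.
- *Arm B is never sampled near nadir.* That is true only of the nominal schedule. A radium-223 visit 7 days early, with blood drawn up to 72 hours before it, puts an Arm B CBC at days 18 to 21. Interim checks are allowed at the physician's discretion (Section 6). Platelets checked for the week 8 biopsy could fall near day 21 in either arm, although the week 5 CBC already meets the 30-day rule in Section 9.1.1. Arm A patients who stop pembrolizumab for toxicity move to Arm B's schedule. These soften the imbalance but do not remove it.
- *No test is planned.* Arms are summarized separately, investigator attribution stands between a laboratory value and the endpoint, and the named special interests (pneumonitis, colitis, severe rash) are not found by CBC. With 30 and 15 patients the intervals are wide: 3/30 has a 90% exact interval of 2.8% to 23.9%, and 0/15 has 0% to 18.1%. So this affects how a table is read and invalidates no inference.

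**Conclusion.** The concern holds for laboratory-detected neutropenia and thrombocytopenia from the first dose through week 13. On the nominal calendar the count is 6 CBCs against 3, with 2 against 0 in the stated nadir window. With equal true toxicity, the by-arm reading for this period tends to favour Arm B.

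The direction follows from the schedule alone. The size does not follow from the documents. A reader might take a figure such as 8% against 3% as an estimate, but it rests on an assumed recovery curve and a borrowed whole-course rate. Recovery at 6 to 8 weeks means that a day-28 count still catches part of the fall, and the excess could be near zero. Nothing is established about direction after week 12, and no planned test is affected. This is a reporting weakness that is cheap to correct.

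**What to change.** Keep the full AE summary in Section 13.8 as planned and add three things:

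1. A supplementary by-arm table of worst CTCAE version 4.0 grade for laboratory neutrophil and platelet values through week 13, using only the CBC times scheduled in both arms: weeks 5, 9 and 13. Describe these as about 4 weeks after radium-223 doses 1 to 3. Week 13 should not be labelled pre-radium, since Arm A's break normally starts then.
2. A separate listing of the Arm A-only values at weeks 4, 7 and 10, so that no safety data are hidden.
3. A note beside the AE table stating the two CBC schedules.

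The supplementary table then rests on 3 scheduled CBCs against 3. The cost is SAP wording, one table and one listing, with no extra blood draws. The downsides are that the common-visit table leaves Arm A's nadir samples out of that comparison, and that it cannot undo the effect of any action prompted by an extra Arm A count, such as supportive care or a delay, on later values.
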